8.4 Deaths

Deaths will be summarized by treatment group:

- All deaths, reasons for death
- Deaths within treatment-emergent period, and reasons for death
- Deaths within extended treatment-emergent period, and reasons for death

A by-patient listing of deaths will be provided for all randomized patients (ITT I/P-risk population and ITT all-risk population).

8.5 Laboratory Parameters

The analysis population for each laboratory test is restricted to patients in the Safety I/P-risk population and the Safety all-risk population who had both a baseline and at least one treatment-emergent measurement of that laboratory test.

8.5.1 Hematology

The following will be summarized by treatment group as baseline CTC grade and worst CTC grade on-treatment per patient: hemoglobin, platelet, white blood counts (WBC), absolute neutrophils count (ANC) and lymphocyte count (LYMP). A table presenting number and percentage of patients with post-baseline CTC grade increased from baseline (any grade, grade 3-4) by treatment group will be provided.

The analyses will be conducted using the treatment-emergent period.

A by-patient listing of these laboratory parameters will be provided.

Eosinophil (EOS)

- Summary of baseline and highest post-baseline EOS will be provided by treatment group:
 - Mean (standard deviation [SD] and standard error [SE]), median, min and max
 - Percent exceeding thresholds: $\geq 10 \times 10^9/L$, $\geq 5 \times 10^9/L$, $\geq 1.5 \times 10^9/L$
 - Time to highest post-baseline EOS: mean (standard deviation [SD]), median, min, max
 - Duration (Weeks) of Sustained Eosinophils $\geq 1.5 \times 10^9/L$: % of patients with eosinophils returned, % patients with duration longer than 6 months, median and 95% CI will be estimated using the KM method

Plot of mean eosinophil (\pm SE) by treatment arm and time.

8.5.2 Serum Chemistry

The following will be summarized by treatment group as baseline CTC grade and worst CTC grade on-treatment per patient: ALT, AST, alkaline phosphatase (ALP), total bilirubin, creatinine, amylase and lipase. A table presenting number and percentage of patients with post-baseline abnormalities increased from baseline (any grade, grade 3-4) by treatment group will be provided.

The analyses will be conducted using the treatment-emergent period.

A by-patient listing of these laboratory parameters will be provided.

8.5.3 Electrolytes

The following will be summarized by treatment group as baseline CTC grade and worst CTC grade on-treatment per patient: sodium (high and low), potassium (high and low), calcium (high and low), and glucose. A table presenting number and percentage of patients with post-baseline abnormalities increased from baseline (any grade, grade 3-4) by treatment group will be provided.

The analyses will be conducted using the treatment-emergent period.

A by-patient listing of these laboratory parameters will be provided.

8.5.4 Additional Analyses

In addition, further analyses on specific laboratory parameters will be performed by treatment group:

Abnormal Hepatic Function Test

The number of patients with the following laboratory abnormalities from on-treatment evaluations will be summarized by treatment group:

- ALT or AST > 3 x ULN, > 5 x ULN, > 10 x ULN and > 20 x ULN
- Total bilirubin > 2 x ULN
- alkaline phosphatase (ALP) > 1.5 x ULN
- Concurrent (within 30 days) ALT or AST > 3 x ULN and total bilirubin > 1.5 x ULN
- Concurrent (within 30 days) ALT or AST > 3 x ULN and total bilirubin > 2 x ULN
- Concurrent (within 30 days) ALT or AST > 3 x ULN and total bilirubin > 2 x ULN and all ALP measurements normal or < 2 x ULN

For identification of concurrent elevations, window for identification of total bilirubin elevation applies to on or after ALT/AST elevation. Window for ALP applies to both before and after ALT/AST elevation.

The analyses will be conducted using the extended treatment-emergent period.

A by-patient listing of these specific abnormalities will be provided.

Abnormal Thyroid Function Test

The number of patients with the following laboratory abnormalities from on-treatment evaluations will be summarized by treatment group:

- TSH value > ULN and
 - with baseline TSH value \leq ULN
 - with at least one FT3/FT4 test value < LLN within 2-week window after the abnormal TSH test
 - with all FT3/FT4 test values \geq LLN within 2-week window after the abnormal TSH test
 - with FT3/FT4 missing within 2-week window after the abnormal TSH test.
- TSH < LLN and
 - with baseline TSH value \geq LLN
 - with at least one FT3/FT4 test value > ULN within 2-week window after the abnormal TSH test
 - with all FT3/FT4 test values \leq ULN within 2-week window after the abnormal TSH test
 - with FT3/FT4 missing within 2-week window after the abnormal TSH test

The analyses will be conducted using the treatment-emergent period.

A by-patient listing of these specific abnormalities will be provided.

8.6 Additional Safety Analyses

8.6.1 Vital Signs

Values at each scheduled visit, change, and percent change from baseline for vital signs, including systolic blood pressure, diastolic blood pressure, pulse, respiration rate, and body temperature will be summarized descriptively.

Criteria for clinically notable vital sign abnormalities are defined in [Table 7](#) below. Abnormal values for patients exhibiting clinically notable vital sign abnormalities will be listed along with their assigned treatment group. Alert vital signs are defined as an absolute value outside the defined range and percentage change > 25%. The abnormal values for patients exhibiting alert vital sign abnormalities will be listed.

Table 7: Criteria for Clinically Notable Vital Sign Abnormalities

Parameter	High Threshold	Low Threshold
Systolic blood pressure	> 160 mmHg	< 90 mmHg
Diastolic blood pressure	> 100 mmHg	< 60 mmHg
Pulse	> 100 bpm	< 60 bpm
Temperature	> 38°C	< 35°C
Respiratory rate	> 24/min	< 12/min

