2.3.7 NKTR-214 and Nivolumab Benefit and Risk Assessment

NKTR-214 has been generally well-tolerated in the clinical studies to date, both as monotherapy as well as in combination with nivolumab, with promising evidence of clinical efficacy and a potentially favorable benefit-risk profile. NKTR-214 has been safely administered in an outpatient setting supported by appropriate clinical monitoring.

Hypotension has been identified as a clinically significant adverse effect of NKTR-214 and can be effectively mitigated by prophylaxis and hydration guidelines. Other risks associated with NKTR-214 include IL-2 mediated AEs (e.g., flu-like symptoms, rash, pruritus, fatigue, hepatic transaminase elevations, and serum creatinine elevation), infusion-related reactions, thyroid dysfunction, eosinophilia, and arthralgia; these AEs are generally mild or moderate in severity and can be monitored and managed in the clinical setting. Cases of thyroid dysfunction (hypothyroidism, hyperthyroidism, thyroiditis), dermatitis, pneumonitis, hepatitis, myocarditis, myositis/myasthenia gravis, and vitiligo/hypopigmentation consistent with immune-mediated mechanism have been observed in patients receiving NKTR-214 plus nivolumab and some of these cases shared clinical characteristics consistent with immune-mediated AEs associated with checkpoint inhibitors.

The continued development of NKTR-214 in combination with nivolumab for the treatment of various cancers is warranted based on a positive benefit-risk profile. In addition, the early efficacy data along with the correlative biomarker showing conversion of PD-L1 negative tumors to PD-L1 positive tumors suggests that the addition of NKTR-214 to a checkpoint inhibitor (nivolumab) may change the tumor microenvironment in PD-L1 negative tumors such that the combination may contribute to anti-tumor activity invoke clinically significant, durable responses with an acceptable safety profile.

In conclusion, the currently available safety data demonstrates that NKTR-214 and nivolumab is a well-tolerated immuno-oncology combination therapy. Given the encouraging clinical activity and manageable and generally non-overlapping toxicity profile, the potential for direct benefit in patients warrants continued evaluation of the combination NKTR-214 and nivolumab in the clinical setting and supports further development of combination of NKTR-214 and nivolumab regimens in patients with cancer.

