6.6 Definitions

- **Baseline:** In general, baseline will be defined as the last assessment result on or before the randomization date (and time if available).

For safety assessment data (laboratory, vital sign): for treated patients, baseline will be defined as the last assessment result on or before the date (and time if available) of the first dose of study treatment; for patients who are randomized but not treated, baseline will be defined as the last assessment result on or before the randomization date.

If there are multiple valid safety assessments on or prior to the first dose of study treatment:

- For laboratory tests, the latest non missing lab value on or before the first dose date (and time if collected) will be used as the baseline in the analyses. If multiple observations exist on the latest collection date (and time if collected), then the first observation is used as baseline.
- For ADA, the record related to the most recent assessment among those records where date (and time if collected) of the ADA assessment being performed for a specific drug is on or before to the date (and time if collected) of the first dose date of that specific drug.

Pre-treatment AEs will be defined as AEs with an onset date prior to, but not including, the day of the first dose of study treatment.

- **Study Day:** There is no study day zero. In general, Study Day 1 is the date of randomization.
 - For post-randomization days, study day is calculated as:
assessment date – randomization date + 1
 - For pre-randomization days, study day is calculated as:
assessment date – randomization date

For safety analysis, study day is calculated and presented based on the first dose date as defined below.

- **First Dose Date:** First dose date will be defined as the date of first dose of study treatment, Cycle 1 Day 1 (C1D1). Note, per protocol, the first dose date may be ≤ 5 days after the date of randomization. If the randomization date and the first dose date is not on the same day, then the date of randomization will be different from C1D1. Safety data will be calculated and presented based on First Dose Date.

- **Treatment-emergent/Extended Treatment-emergent Period:**

For patients on treatment, both the treatment-emergent period and the extended treatment-emergent period will be defined as the period of time on or after the day (and time, if collected and not missing) of the first dose of study treatment.

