8.3.2 Other Safety Observations (OSO) for NKTR-214

Other safety observations (OSO) for NKTR-214 consists of the following:

- IL-2 mediated AEs
 - Flu-like symptoms
 - Rash and pruritus
 - Fatigue/asthenia
 - Arthralgia
 - Elevated hepatic transaminases
 - Elevated serum creatinine
 - Eosinophilic disorders
 - Hypotension
 - Syncope
- Infusion-related reaction (IRR, same day or next day post study drug administration)
- Cytokine release syndrome/cytokine storm (CRS)
- Capillary leak syndrome (CLS)
- Tachyarrhythmias (including supraventricular and ventricular)

All analyses will be conducted in the Safety I/P-risk population and the Safety all-risk population by treatment arm using the treatment-emergent period.

Table 6 lists the planned analyses for each category of OSO for NKTR-214.

- 1) Overall summary of OSO by worst CTC grade presented by category/PT (any grade, grade 3-4, grade 5).
- 2) Overall summary of serious OSO by worst CTC grade presented by category/PT (any grade, grade 3-4, grade 5).
- 3) Overall summary of OSO leading to discontinuation of any study drug by worst CTC grade presented by category/PT (any grade, grade 3-4).
- 4) Overall summary of OSO leading to discontinuation of NKTR-214 by worst grade presented by category/PT (any grade, grade 3-4). This summary will be conducted for Arm A patients.
- 5) Time-to onset of OSO (any grade, grade 3-5) by category
- 6) Overall summary of OSO by Cycle by Worst Grade by category (any grade, grade 3-5) (for Arm A only, and cycle is every 3 weeks in this analysis)

Time-to onset analyses are restricted to treated patients who experienced at least one OSO in the specific category.

For IRR, events that start after study drug administration on the same day or next day will be included. If AE onset time is available, the time information will be used to exclude events that start before study drug administration; otherwise, AEs that start on the same day as study drug administration will be included. Analysis on IRR will only be performed for Arm A.

A by-patient listing of OSO will be provided.

Table 6: Planned Analyses for OSO for NKTR-214

Table Numbers ^a	Tachyarrhythmias	Syncope	CRS CLS	Infusion-related reaction (same day or next day post study drug administration) (For Arm A only)	Flu-like symptoms; Rash and pruritus; Fatigue/asthenia; Arthralgia; Elevated hepatic transaminases; Elevated serum creatinine; Eosinophilic disorders; Hypotension
1), 2)	Yes	No	No	Yes	Yes
3), 4)	Yes	No	No	Yes	Yes

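### The 25% change condition in the SAP's alert rule cannot work for temperature in °C, and the rule gives neither the reference nor the direction of the change

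*SAP*

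**What the plan says.** SAP section 8.6.1 plans three outputs for vital signs:

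- Descriptive summaries by visit, including "change, and percent change from baseline for vital signs".
- A listing of *clinically notable* abnormalities, meaning any value beyond the Table 7 limits, shown with treatment group. For example: "Temperature > 38°C < 35°C" and "Systolic blood pressure > 160 mmHg < 90 mmHg".
- A listing of *alert* abnormalities: "Alert vital signs are defined as an absolute value outside the defined range and percentage change" above 25%.

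The alert sentence makes no exception for any parameter. It does not say what the change is measured from, or whether a fall counts. SAP section 6.6 supplies a baseline for vital signs in those who are dosed: "baseline will be defined as the last assessment result on or before the date (and time if available) of the first dose of study treatment". The alert sentence does not refer to it.

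The documents identify both fever and hypotension as effects of the drug. SAP section 8.3.2 lists "Flu-like symptoms" among the other safety observations. Protocol section 2.2.4 counts pyrexia within that term and reports it in 20 of 28 monotherapy patients (71.4%). Protocol section 2.3.7 states: "Hypotension has been identified as a clinically significant adverse effect of NKTR-214".

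**The concern.** A percentage change is meaningful only on a scale with a true zero. Blood pressure, pulse and respiratory rate have one; temperature in °C does not, and the whole clinical range is a small fraction of the reading itself. Because the two conditions are joined by *and*, the 25% requirement overrides the 38 °C limit in Table 7.

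An empty temperature section would then follow from the rule and say nothing about the patients. A reader of the study report could take it as evidence that no marked fevers occurred on a drug for which fever is expected.

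The missing reference and direction are a separate problem. The programmer must decide whether a fall of more than 25% counts, and one literal reading removes every low blood-pressure alert.

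**Working it through.** The documents give no figure on this point to reproduce, so the check is arithmetic on the rule.

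**Inputs.** Table 7 limits: temperature above 38 or below 35 °C; systolic pressure below 90 mmHg; diastolic pressure below 60 mmHg. Change threshold: 25% (SAP 8.6.1). Reference: baseline *b*, inferred from the first sentence of 8.6.1. Baseline values are assumptions, because the documents give no distribution: 36.0 to 37.5 °C for temperature, with illustrative values for blood pressure.

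**Formulas, counting change in either direction.**
- High alert: value > max(upper limit, 1.25*b*).
- Low alert: value < min(lower limit, 0.75*b*).

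**Temperature.**

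| Baseline (°C) | Fever alert needs above | Low alert needs below | Change at 40 °C | Change at 42 °C |
|---|---|---|---|---|
| 36.0 | 45.0 | 27.0 | +11.1% | +16.7% |
| 36.5 | 45.6 | 27.4 | +9.6% | +15.1% |
| 37.0 | 46.25 | 27.75 | +8.1% | +13.5% |
| 37.5 | 46.9 | 28.1 | +6.7% | +12.0% |

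For 42 °C to exceed a 25% rise, baseline would have to be below 42/1.25 = 33.6 °C. The result does not depend on where in the assumed range the baseline lies.

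**Systolic pressure.** The 25% condition stops mattering once 0.75*b* ≥ 90, that is at *b* ≥ 90/0.75 = 120 mmHg. From there up, every value below 90 is an alert. At lower baselines the alert needs:
- *b* = 115: below 0.75 × 115 = 86.25 mmHg
- *b* = 110: below 0.75 × 110 = 82.5 mmHg
- *b* = 100: below 0.75 × 100 = 75 mmHg

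So 80 mmHg is flagged from 110 (−27.3%) but not from 100 (−20.0%).

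**Diastolic pressure.** The corresponding baseline is 60/0.75 = 80 mmHg. From a baseline of 70, an alert needs a value below 0.75 × 70 = 52.5 mmHg.

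**Direction.** In the alert sentence, *absolute* describes the value, not the change. If the change is signed, a fall from 120 to 80 mmHg is −33.3%, which is not greater than +25%. On that reading no low value of any parameter could be an alert.

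**The case against.** The strongest reply is that nothing is lost. The listing of clinically notable values in the same section has no percentage condition, so every temperature above 38 °C and every systolic value below 90 mmHg appears there with treatment group. SAP section 8.3.2 and its Table 6 analyse flu-like symptoms and hypotension by worst grade, seriousness, discontinuation, time to onset and cycle. The SAP gives the alert listing no stated purpose and no decision role. All of this stands, and it is why the point is minor. It does not rescue a temperature flag that no fever can trigger.

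A reader might infer that the alert listing also omits hypotension. The rule does not do that when falls are counted. The 25% condition has no effect at a baseline systolic pressure of 120 mmHg or more, and deeper falls are still flagged below that. Requiring a material fall as well as a low value is a coherent narrower tier. Dropping the requirement would only repeat the clinically notable listing.

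A reader might also infer that no survivable temperature could be an alert. That is secure for fever. On the cold side the trigger is about 27 to 28 °C, and the documents do not settle what that means clinically.

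One limit on the reply is fair to record. Under Protocol section 8.1 a vital-sign abnormality becomes an adverse event only if the investigator judges it clinically significant, so the adverse-event analyses do not fully replace a flag computed from the readings. The clinically notable listing already provides such a flag.

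**Conclusion.** The point holds in two parts. First, the 25% condition makes the temperature alert unreachable for any realistic fever: over assumed baselines of 36.0 to 37.5 °C, the trigger lies above 45.0 to 46.9 °C. Second, the alert sentence leaves the reference and direction of the change open, and a signed reading would remove all low blood-pressure alerts.

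The consequence is confined to one descriptive listing. No endpoint, alpha level, power calculation, adverse-event table or patient decision depends on it. The documents do not support reading this as a failure to detect fever or hypotension. The temperature result rests on two assumptions, that the change is measured from baseline and that baselines are near normal.

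**What to change.** In SAP section 8.6.1:

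1. State that the percentage change is from the section 6.6 baseline and counts in either direction.
2. For temperature, replace the 25% condition with an absolute change from baseline in °C, of a size the sponsor specifies. Alternatively, remove the condition for temperature; the alert criterion for that parameter then equals the Table 7 limits and repeats the clinically notable listing. The absolute change is the more informative option.
3. Leave the blood-pressure criterion as it is, once its direction is stated.

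The cost is a one-sentence edit and a somewhat longer alert listing. No new data are needed.

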9.0 COVID-19 RELATED ANALYSES

9.1 Study Conduct

9.1.1 Patients Impacted

A brief high-level summary of patients impacted by coronavirus disease 2019 (COVID-19) will be provided by treatment group for the Safety IMDC I/P-risk Analysis Set and Safety IMDC All-risk Analysis Set. This summary will present the number and percentage of patients with any incidence in each of the categories listed below due to COVID-19 and any reason, where total number of patients in corresponding treatment group will be used as denominator for percentage calculation:

- Any positive test of COVID-19
- Received COVID-19 vaccine (type/manufacturer of vaccine, e.g., RNA vaccine from Pfizer) during treatment
- Missed study visit
- Missed at least 9 weeks of doses (For Arm A, missing 2 consecutive doses for NKTR-214 and nivolumab means no infusion in 9 weeks, which is comparable to missing 9 weeks of doses for Arm B).Delayed scan
- Missed scan (any missed scan, 2 scans missed, ≥ 3 scans missed)
- Study treatment discontinuation
- Study discontinuation
- Death
- Study treatment discontinuation

9.1.2 Multiple Incidences

Number of unique incidences per person in each of the categories listed below due to COVID-19 will be summarized by country and by treatment group using descriptive statistics:

- Missed study visit
- Missed at least 9 weeks of doses Delayed scan
- Missed scan

A table showing total number of occurrences (unique incidences) in each category by treatment group will be provided.

A listing of all COVID-19 impact data collected will be created.

9.2 Impacts on Efficacy Results

Supplementary analyses for ORR and OS may be performed to estimate the treatment effects without the COVID-19 impact if needed.

9.3 Impacts on Safety Results

By-patient listing for COVID-19 related adverse events will be provided for the Safety Analysis Set. If sample size allows (e.g., > 10 per treatment group), COVID-19 related TEAEs can be summarized by worst CTC grade and treatment group for COVID-19 infected patients. Impact of COVID-19 vaccines on study drug dosing and adverse events may be further explored.

If central clinical laboratory data was missing for some patients in some visits due to COVID-19, local laboratory data may be collected in place of missed central laboratory data. In such a case, central laboratory and local laboratory data may be combined for the lab related analysis. Specific considerations are described as follows:

1. For summary of post-baseline laboratory toxicity worsening from baseline

All (scheduled and unscheduled) central and local laboratory data will be included. The central and local laboratory data will be graded according to their corresponding laboratory normal ranges (central laboratory normal range for central laboratory data, local laboratory normal range for local laboratory data). If the baseline value is involved in the derivation of toxicity grade based on CTCAE 5.0, the corresponding baseline value for central and local laboratory will be used as reference (central laboratory toxicity grade based on central laboratory baseline value, local laboratory toxicity grade based on local laboratory baseline value). If a corresponding baseline value is not available, for that particular laboratory value, the toxicity grade will be derived assuming the baseline value is normal, thus the grade will be derived based on corresponding normal range only.

In summary table, the baseline toxicity grade will be based on central laboratory data if the central laboratory data is available; otherwise (central laboratory data is not available), then the baseline grade will be based on local laboratory if available. The post-baseline worst toxicity grade will be based on the worst grade of both central and local laboratory data.

2. For summary of abnormal hepatic function and summary of abnormal thyroid function

All (scheduled and unscheduled) central and local laboratory data will be included. The central and local laboratory data (AST, ALT, total bilirubin, TSH, FT3, FT4) will be summarized according to their corresponding laboratory normal ranges (central laboratory normal range for central laboratory data, local laboratory normal range for local laboratory data).

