- a. Absolute neutrophil count (ANC) $\geq 1500/\mu\text{L}$ ($\geq 1000/\mu\text{L}$ for patients with known or suspected diagnosis of benign ethnic neutropenia) after at least 14 days without growth factor support
 - b. Platelet count $\geq 100 \times 10^3/\mu\text{L}$ after at least 14 days without transfusion
 - c. Hemoglobin ≥ 9.0 g/dL after at least 14 days without transfusion or growth factor support
 - d. Serum creatinine $\leq 1.5 \times \text{ULN}$ (or estimated creatinine clearance ≥ 40 mL/min)
 - e. Aspartate aminotransferase (AST) and alanine transaminase (ALT) $\leq 3 \times \text{ULN}$
 - f. Total bilirubin $\leq 1.5 \times \text{ULN}$ (total bilirubin $\leq 2 \times \text{ULN}$ if associated with hepatobiliary metastases or Gilbert's syndrome)
 - g. Urine protein creatinine ratio (UPCR) < 1.0 (< 113 mg/mmol) or 24-hour urine protein < 1 gram (g)
- Note: Patients with severe hepatic impairment (Child-Pugh Class C) are ineligible.
10. A documented left ventricular ejection fraction (LVEF) $> 45\%$ using standard echocardiogram or multigated acquisition (MUGA) scan test within 60 days prior to randomization.
11. Oxygen saturation $\geq 92\%$ on room air
12. Clinically significant toxic effect(s) of any prior anticancer therapy (if applicable) must be Grade 1 or resolved (except alopecia and sensory neuropathy). If the patient received major surgery, they must have complete wound healing and recovered from any complication from the surgery.
13. Reproductive Status
- a. Women of childbearing potential (WOCBP) must have a negative serum or urine pregnancy test (minimum sensitivity 25 IU/L or equivalent units of human chorionic gonadotropin [hCG]) within the 28 days prior to randomization
 - b. Women must not be breastfeeding

- c. Women of childbearing potential must agree to follow instructions for method(s) of contraception for the duration of study treatment and for 5 months post treatment completion. Women should use an adequate method(s) of contraception as indicated in [Appendix 4](#).
- d. Men who are sexually active with WOCBP must agree to follow instructions for method(s) of contraception ([Appendix 4](#)) for the duration of study treatment and 3 months post NKTR-214 completion. In addition, male patients must refrain from sperm donation during this time.

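### SAP 9.3 grades a local laboratory value that has no local baseline as if baseline were normal, even when an abnormal central baseline is on record, so the worsening-from-baseline tables can misstate worsening in either direction

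*SAP*

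**What the plan says.** The rule is in SAP 9.3, item 1. It applies when central results are missed because of COVID-19, in which case "local laboratory data may be collected in place of missed central laboratory data" and the two sources may be combined. Once they are combined, all local values enter, scheduled or not.

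- **Scope.** The baseline rule is limited by "If the baseline value is involved in the derivation of toxicity grade based on CTCAE 5.0". Neither document lists those tests or gives the grade cut-points.
- **Reference.** Each laboratory is its own reference: "local laboratory toxicity grade based on local laboratory baseline value", and likewise for central values.
- **Fallback.** If a value has no baseline from its own laboratory, "the toxicity grade will be derived assuming the baseline value is normal, thus the grade will be derived based on corresponding normal range only". Nothing allows the other laboratory's baseline to be used.
- **Baseline column.** "the baseline toxicity grade will be based on central laboratory data if the central laboratory data is available"; otherwise local.
- **Post-baseline column.** The worst grade from either laboratory.

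SAP 8.5 restricts each laboratory analysis to patients "who had both a baseline and at least one treatment-emergent measurement of that laboratory test". SAP 8.5.2 then counts patients whose chemistry grade rose from baseline (any grade, and Grade 3-4) for ALT, AST, ALP, total bilirubin, creatinine, amylase and lipase.

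**The concern.** SAP 8.5 admits only patients with a baseline for the test. A tabulated patient whose local value lacks a local baseline must therefore normally have a central one. SAP 9.3 uses that central baseline for the baseline column and ignores it when grading the local value. If it is abnormal, the local value is graded against a reference that the trial knows to be wrong, and a central value from the same patient is graded against the right one. Because the worst grade is kept, one such local value can set the patient's entry.

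Protocol 2.3.5 lists hepatic transaminase and serum creatinine elevations among the identified risks of NKTR-214, and ALT, AST and creatinine are all in the SAP 8.5.2 table. A patient's place in the any-grade or Grade 3-4 row should not depend on which laboratory ran the sample.

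**Working it through.** The plan gives no figure to reproduce here, so the check is on the logic of the rule and a worked grading example.

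**Inputs.** Protocol 4.1, criterion 9, allows ALT and AST up to 3 x ULN at entry. It allows bilirubin up to 1.5 x ULN (2 x with hepatobiliary metastases or Gilbert's syndrome) and creatinine up to 1.5 x ULN, or higher if estimated clearance is at least 40 mL/min.

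**Size of the shift.** Exactly, value/ULN = (value/baseline) x (baseline/ULN). Ignoring an abnormal baseline therefore multiplies the graded ratio by baseline/ULN. At the entry limits this is 3.0 for ALT and AST, 1.5 to 2.0 for bilirubin, and 1.5 or more for creatinine, in each case only if the test's grade depends on baseline.

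**Worked grades.** These cut-points are assumptions, since the documents give none:

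- Baseline normal: Grades 1 to 4 above 1, 3, 5 and 20 x ULN.
- Baseline abnormal: Grade 1 from 1.5 x baseline, then Grades 2 to 4 above 3, 5 and 20 x baseline.

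Baseline and later values below are multiples of ULN.

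| Central baseline | Later value | Value/baseline | Grade if run centrally | Grade if run locally, no local baseline |
|---|---|---|---|---|
| 2.5 | 2.5 | 1.0 | 0 | 1 |
| 2.5 | 3.25 | 1.3 | 0 | 2 |
| 3.0 | 3.3 | 1.1 | 0 | 2 |
| 2.5 | 6.0 | 2.4 | 1 | 3 |

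Whether a row counts as worsening depends on how the baseline value is graded, which the SAP does not say.

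- **Baseline graded on the normal range.** Every baseline above is Grade 1. The unchanged value in row 1 shows no worsening from either laboratory. Rows 2 and 3 show worsening (1 to 2) only if run locally. Row 4 goes 1 to 3 locally and 1 to 1 centrally.
- **Baseline graded against itself.** Every baseline above is Grade 0. Run locally, all four rows show worsening, including the unchanged value (0 to 1). Run centrally, only row 4 does (0 to 1).

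**Range.** Take baseline b spread evenly over about 1 to 3 x ULN and fold change f evenly over 0.5 to 1.5, an area of 2. All these values are at or below 1.5 x baseline.

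- Baseline graded on the normal range: a local value is flagged when b x f > 3. The area is 1.5 - 3 ln(1.5) = 0.284, and 0.284/2 = 14%.
- Baseline graded against itself: flagged when b x f > 1. The area is (1.5 - ln 2) + 1 = 1.807, and 1.807/2 = 90%.

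These shares show how far the result depends on the unstated convention. They are not estimates for this trial.

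**Opposite direction.** Suppose a test is graded on multiples of baseline even when baseline is normal, with an assumed cut at 1.5 x baseline. A rise from 0.6 to 1.0 x ULN is 1.0/0.6 = 1.67 x baseline. It is graded if run centrally. It is missed if run locally without a local baseline, because it does not exceed ULN.

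**The case against.** A reader might infer that local baselines will often be absent. The documents do not support that. Protocol 8.15, Appendix 3 and the Cycle 1 Day 1 column of Tables 2 and 3 require local testing before the first dose in both arms, and Appendix 3 lists AST, ALT, total bilirubin and creatinine. Under SAP 6.6 such a result can serve as baseline. ALP is in the SAP 8.5.2 table but not on that list, so it is more exposed if its grade depends on baseline. On the other side, no section says the required local results routinely reach the database, and SAP 9.3 describes local data as a substitute for missed central data. Frequency is therefore unknown.

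A reader might also infer that the tables will report false worsening. That is possible but not automatic: an unchanged value is not flagged if baseline is graded on the normal range, and worsening can also be missed. Which tests are baseline-dependent is likewise not in the documents.

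The rise from 2.5 to 6 x ULN is real. If baseline is graded on the normal range, grading the later value against baseline would give 1 to 1 and remove the patient from the worsening count. This stands: changing the fallback without stating how baseline is graded leaves the two columns on different references.

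The scope limits also stand. Combining is optional and triggered by COVID-19, the rule is the same in both arms, and no primary or key secondary endpoint is touched. The abnormal hepatic function summaries (SAP 8.5.4 and 9.3, item 2) and the potential DILI definition (Protocol 8.13) use multiples of ULN and are unaffected.

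Same-laboratory references do avoid cross-laboratory comparison. But SAP 9.3 already compares across laboratories when it takes the worst grade from either and sets it beside a central baseline grade.

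**Conclusion.** The point holds in a limited form. SAP 9.3, item 1, sets aside a known baseline, so for baseline-dependent tests the same value can be graded differently by laboratory, and the worst-grade rule carries that into the worsening tables in either direction. The shift in the graded ratio is exactly baseline/ULN, up to 3-fold for ALT and AST at the entry limit. The grade changes in the worked example rest on assumed cut-points and an unstated convention for grading baseline. The number of patients affected cannot be derived; it depends on how much local data is combined and how many of those values lack a recorded local baseline. The consequence is confined to descriptive safety tables. The change is still worth making, because the rule discards known information and the correction is cheap.

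**What to change.** In SAP 9.3, item 1:

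1. Replace the fallback. When no same-laboratory baseline exists, take the patient's other available baseline (normally central) as a multiple of its own ULN or LLN, and compare it with the local value as a multiple of the local limit. Assume a normal baseline only if neither laboratory has one; SAP 8.5 already excludes such patients from these tables.
2. State how the baseline value itself is graded for baseline-dependent tests, so that the baseline and post-baseline columns are comparable.

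The cost is two sentences in the SAP and a small change to the grading program. The downside is that multiples of the normal limit are treated as comparable between laboratories. A sensitivity table leaving out local values without a local baseline would show whether this matters.
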